5.12 Safety Analyses

The safety analyses will be presented by the treatment received for the safety population.

5.12.1 Adverse Events

AE analyses will be presented by the treatment received for the safety population. Tabulations will be presented overall and by standard of care (Yes, No).

AEs will be collected from the time of informed consent through completion of the participant's last study visit.

A treatment emergent adverse event (TEAE) is defined as:

- Any AE that has an onset on or after the first dose of study drug through completion of the last study visit.

QMD Ref: [REDACTED]	Governing QMD: [REDACTED]
Confidentiality Statement	
This document is the property of [REDACTED] without prior approval from [REDACTED]	and may not be duplicated, copied, altered or removed from company or in compliance with [REDACTED]

		Controlled Quality Management Document Sponsor: Pliant Therapeutics Inc Protocol Number: PLN-74809-IPF-205
STATISTICAL ANALYSIS PLAN		

- Any pre-existing AE that has worsened in severity on or after the first dose of study drug through completion of the last study visit.

AEs occurring prior to first dose are considered nontreatment emergent and will be listed only.

The Investigator will determine the relationship of the AE to treatment (related, not related). A study drug-related AE is defined as an AE as being possibly or probably related to the study drug. If an AE has missing relationship it is assumed to be related to the study drug for analysis purposes. Same rule is applied to study procedure-related AE.

Severity of the AE will be graded using the Common Terminology Criteria for Adverse Events (CTCAE) grading system (Version 5.0): Grade 1 (Mild), Grade 2 (Moderate), Grade 3 (Severe), Grade 4 (Life-Threatening), Grade 5 (Fatal). Grade 3 (Severe) will be assumed for an AE with missing grade.

An overall summary of AEs (incidence and number of events) will be presented by treatment group and overall, for the following:

- TEAEs
- TEAEs Related to Study Drug
- TEAEs Related to a Study Procedure
- Serious TEAEs
- Serious TEAEs Related to Study Drug
- TEAEs of CTCAE Grade 3 or Higher
- TEAEs of CTCAE Grade 3 or Higher Related to Study Drug
- TEAEs Leading to Interruption of Study Drug
- TEAE Leading to Early Discontinuation of Study
- TEAEs Leading to Early Termination from Study
- TEAEs Leading to Death

Summaries of TEAEs (by participant incidence) will be presented by system organ class and preferred term, by treatment group and overall, for the following:

- TEAEs
- TEAEs Related to Study Drug
- Serious TEAEs
- Serious TEAEs Related to Study Drug
- TEAEs Related to a Study Procedure
- TEAEs of CTCAE Grade 3 or Higher
- TEAEs of CTCAE Grade 3 or Higher Related to Study Drug
- TEAEs Leading to Interruption of Study Drug

QMD Ref: [REDACTED]	Governing QMD: [REDACTED]
Confidentiality Statement	

This document is the property of [REDACTED] and may not be duplicated, copied, altered or removed from company without prior approval from [REDACTED] or in compliance with [REDACTED].

		Controlled Quality Management Document	
		Sponsor:	Pitant Therapeutics Inc
		Protocol Number:	PLN-74809-IPF-205
STATISTICAL ANALYSIS PLAN			

- TEAEs Leading to Early Discontinuation of Study Drug (action taken with study treatment as 'Drug Withdrawn' or 'Drug Interrupted Permanently')
- TEAEs Leading to Early Termination from Study
- TEAEs Leading to Death
- TEAEs by System organ class, Preferred term and Maximum Grade (incidence only)
- ECG-Related or Potentially Cardiac-Related TEAEs (incidence only)

In addition, TEAEs by preferred term will also be summarized.

In addition, listings of all reported AEs and SAEs will be provided in Appendix 16.2.7 of the CTR:

- AEs
- TEAEs Leading to Early Discontinuation of Study Drug
- TEAEs Leading to Early Termination from Study
- TEAEs Leading to Death
- Serious AEs

System organ class will be presented in descending order of frequency in the PLN-74809 group and then alphabetically. Preferred terms will be displayed in descending order of frequency in the PLN-74809 group and then alphabetically.

For the summary by severity, participants reporting more than one AE per system organ class and preferred term will only be counted once for the most severe event.

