3 INVESTIGATIONAL PLAN

3.1 Overall Study Design and Plan

This is a Phase 2a, single-center, randomized, double-blinded, placebo-controlled study to evaluate type 1 collagen deposition in the lungs following once-daily (QD) treatment with 160 mg PLN-74809 for 12 weeks in participants with IPF.

The study consists of an up to 28-day screening period, a 12-week treatment period, and a 2-week (± 3 days) post treatment follow-up period.

Potential participants who provide written informed consent will be screened for study eligibility up to 28 days before administration of the first dose of study drug. Approximately 12 eligible participants will be randomized in a 2:1 ratio (160 mg PLN-74809 vs placebo; 8 receiving PLN-74809 and 4 receiving placebo) on Day 1 (Visit 3). Study treatment will be administered once daily for 12 weeks. Randomization will be stratified by use of standard of care (SoC) IPF therapy with pirfenidone or nintedanib (SoC use; yes or no).

^{68}Ga -CBP8 PET/MRI scans will be conducted within 7 days prior to baseline and at or within 7 days prior to Week 12, as indicated in the Schedule of Events ([Appendix 1](#)).

Participants who discontinue study drug for safety reasons prior to completion of 12 weeks of treatment will be encouraged to remain in the study to complete all remaining assessments; if this is not feasible, they will be asked to return to the clinic for an Early Termination (ET) visit for follow-up evaluations. If a participant elects to withdraw from the study after the 6th week of randomization, an end of participation ^{68}Ga -CBP8 PET/MRI will be offered to the participant to enhance appropriate data capture.

Potential acute exacerbations, respiratory-related hospitalizations, and/or respiratory-related deaths will be reviewed by an adjudication committee.

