5 STUDY DRUG AND ACCOUNTABILITY

5.1 Description of Study Drug

5.1.1 *Study Drug*

The zwitterion PLN-74809-000, and the phosphate salt PLN-74809-020 are derivatives of the parent form PLN-74809. Both are formulated as immediate-release tablets. In this study, the phosphate form will be tested, hereafter referred to as PLN-74809.

PLN-74809 drug product is supplied as 80-mg immediate release tablets. The PLN-74809 tablets are manufactured by dry granulation with standard excipients (microcrystalline cellulose, mannitol, crospovidone, magnesium stearate, and butylated hydroxytoluene), tablet compression, and spray coating of tablets.

5.1.2 *Placebo*

A corresponding matching placebo will be provided.

5.1.3 *PET Tracer*

The ^{68}Ga -CBP8 PET/MRI tracer is not considered a study treatment but is an investigational tool used during the PET procedure for obtaining the images necessary for this trial. ^{68}Ga -CBP8 is given as an intravenous injection within 7 days prior to baseline and at or within 7 days prior to Week 12. The radiochemical dose is up to 12.9 mCi but in practice, the dose has averaged 5.5 mCi per subject.

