12.6 Secondary Endpoints

12.6.1 *Secondary Safety Endpoint*

- Assessment of the safety and tolerability of PLN-74809 in IPF participants

Safety data from all participants who received at least one dose of study drug will be incorporated into the final safety analysis. Further details of the safety analyses will be provided in the SAP. AEs will be collected from the time the participant signs the ICF until the last study visit. Treatment-emergent adverse events (TEAEs) are defined as AEs that emerged or worsened in severity after the first administration of study drug.

AEs will be coded using the Medical Dictionary for Regulatory Activities (MedDRA®). All AEs will be graded for severity per the CTCAE grading scale and listed by participant and summarized by treatment.

The incidence of AEs, the incidence of TEAEs, the incidence of treatment-related AEs, and the severity of AEs will be summarized by system organ class, preferred term, and maximum severity. In cases where a participant reports multiple occurrences of the same event (preferred term), the greatest severity will be included in the summary. The number and percentage of participants with SAEs and treatment-related SAEs, and the number and percentage of participants who withdraw due to an AE will be tabulated by study treatment and dose.

Clinical laboratory test parameters will be listed, using the CTCAE grading scale, for individual participants, with values outside the reference ranges flagged. The incidence of treatment-emergent laboratory abnormalities will be summarized by severity. Summary statistics will be calculated for each parameter.

Individual ECG results will be listed for each participant. Summaries of ECGs will include changes from baseline for each parameter. The number and percentage of participants with abnormal ECGs will be summarized by treatment.

Vital sign measurements other laboratory tests, concomitant medications, medical history and changes in physical examinations at each time point will be listed by participant.

Concomitant medications will be coded using the most current World Health Organization drug dictionary available.

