5.2.10 Conventions for Missing and Partial Dates

Dates (historical or during study conduct) will only be imputed if a full date is needed for a calculation or to support a definition.

QMD Ref: [REDACTED]		Governing QMD: [REDACTED]
Confidentiality Statement		

This document is the property of [REDACTED], and may not be duplicated, copied, altered or removed from company without prior approval from [REDACTED] or in compliance with [REDACTED].

		Controlled Quality Management Document
	Sponsor:	Pliant Therapeutics Inc
	Protocol Number:	PLN-74809-IPF-205
STATISTICAL ANALYSIS PLAN		

All dates presented in the individual participant listings will be presented as recorded on the electronic case report form (eCRF).

Missing / Partial Start / Stop Date of Adverse Events, Medical History and Concomitant Medication

Missing and partial start dates will be imputed solely for the purpose of determining whether an AE is treatment-emergent, medical history is ongoing at screening, or a medication is concomitant to study drug.

Partial or missing stop date will be imputed as follows:

If the stop date is completely missing and the event has resolved, or the participant has stopped taking the concomitant medication, the stop date will be imputed as the date of the participant's last clinic visit in the study.

- If only the year is known, the stop date will be imputed as "31-Dec" of that year or as the date of the participant's last clinic visit in the study if in the same year.
- If the month and year are known, the stop date will be imputed as the last day of that month unless the stop date corresponds to the same month as the participant's last clinic visit in which case the date of participant's last clinic visit in the study will be used instead.

Missing start date will be imputed as follows:

- If the stop date occurs on or after the start of study drug or the event / concomitant medication is ongoing, the start date will be imputed as the date of the first dose of study drug.
- If the stop date occurs before the start of study drug, the start date of the event / concomitant medication will be imputed as the participant's screening date or the stop date of the event / concomitant medication whichever the earlier.

Partial start date (year present, but month and day missing)

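### SAP 5.12.1 counts procedure-related AEs only if treatment-emergent, so reactions to the pre-baseline tracer and gadoterate scan that start before first dose and do not worsen are listed but not tabulated

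*SAP*

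**What the plan says.** **Timing of the scans.** Protocol 3.1 states that the PET/MRI "scans will be conducted within 7 days prior to baseline and at or within 7 days prior to Week 12". The Schedule of Events puts the first at Visit 2, Day -7 to Day -1. Randomization and first dose follow on Day 1 (Protocol 6.4). Protocol 7.10.2 gives gadoterate contrast at each session.

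**Status of the tracer.** Under Protocol 5.1.3 the "tracer is not considered a study treatment but is an investigational tool used during the PET procedure". Protocol 8.4 has the investigator judge causality against study drug (PLN-74809 or placebo) and, separately, against study procedures.

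**AE tables.** SAP 5.12.1 collects AEs from consent. It defines a TEAE in two limbs: "Any AE that has an onset on or after the first dose of study drug" and "Any pre-existing AE that has worsened in severity on or after the first dose of study drug", each running through the last study visit. Of everything else it says "AEs occurring prior to first dose are considered nontreatment emergent and will be listed only". The overall summary and the system organ class/preferred term tables each have one procedure-related entry, "TEAEs Related to a Study Procedure".

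**Protocol commitment.** Protocol 12.6.1 says "The incidence of AEs, the incidence of TEAEs, the incidence of treatment-related AEs, and the severity of AEs will be summarized", so AEs and TEAEs are separate items. Every AE table described in SAP 5.12.1 is a TEAE table. SAP Section 9, which records changes from the protocol, does not mention this.

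**The concern.** A treatment-emergent window suits an oral drug that starts on Day 1. Here it is also applied to an intravenous procedure whose first exposure always comes before Day 1. Because the tracer is not study treatment, a reaction to it or to the contrast belongs naturally in the procedure-related category. An acute reaction that begins and resolves at Visit 2 cannot enter that category's tables.

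The practical risk is a misleading zero. A reader of the study report who sees no procedure-related events would reasonably take that to cover both scans, when acute reactions to the first were never eligible to be counted. The serious-event tables are also limited to TEAEs, so a serious reaction at Visit 2 would likewise be listed and not tabulated.

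The SAP seems to want a cautious procedure-related count, since an AE with missing relationship to procedure is treated as related. The protocol also excludes people with a history of anaphylaxis to intravenous drugs (4.3, exclusion 17), although the study drug is oral. The window works against that caution.

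**Working it through.** **1. Scans per participant.** Protocol 7.10.1 gives up to 22 mSv in total and 11 mSv per administration. 22 / 11 = 2 administrations, which agrees with the two scan times in Protocol 3.1.

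**2. Share of planned scans before first dose.** About 12 participants are planned (Protocol 12.2).
- Planned scans: 12 × 2 = 24.
- Before first dose: 12 × 1 = 12.
- Share: 12 / 24 = 50%.

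Among scans actually performed, the share rises if later scans are missed or if someone is scanned but not randomized:
- two second scans missed: 12 / 22 = 54.5%;
- one extra person scanned and not randomized: 13 / 25 = 52%. That person is also outside the safety population (SAP 5.1.3).

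**3. Where a first-scan reaction goes under the SAP's rules.**

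| Reaction to the first scan | Rule | Display |
|---|---|---|
| Known onset before first dose, no later worsening | SAP 5.12.1, nontreatment-emergent | Listing only |
| Onset before first dose, worsens on or after it | SAP 5.12.1, second limb | Tables and listing |
| Delayed, onset on or after first dose | SAP 5.12.1, first limb | Tables and listing |
| Start date missing; event ongoing or stops on or after first dose | SAP 5.2.10: "the start date will be imputed as the date of the first dose of study drug" | Tables and listing |
| Partial start date in the month of first dose (or year only, same year); ongoing or stops on or after first dose | SAP 5.2.10, same imputation | Tables and listing |
| Participant scanned but never dosed | Outside safety population (SAP 5.1.3); non-randomized participants are listed last (SAP 5.3.6) | Listing only |

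The gap is therefore the first and last rows. The first row is the usual course of an acute reaction with a recorded date.

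**4. What counting 12 rather than 24 scans means (illustration).** The documents give no reaction rate. I assume that scans are independent and have a common per-scan risk p.

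If no reactions are seen in n scans, the one-sided 95% upper bound on p is 1 − 0.05^(1/n):
- n = 12: 22.1%;
- n = 24: 11.7%.

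The chance of at least one reaction among the covered scans is 1 − (1 − p)^n:

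| Assumed p | 12 scans | 24 scans |
|---|---|---|
| 1% | 11% | 21% |
| 2% | 22% | 38% |
| 5% | 46% | 71% |
| 10% | 72% | 92% |

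These figures show what covering both scans would add. They do not estimate a bias in this trial.

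**The case against.** **The restriction is coherent for the stated objective.** The secondary objective is the safety of PLN-74809, and SAP 2.2.2 names treatment-emergent AEs and SAEs. Events before randomization cannot be caused by study drug, so keeping them out of drug-related comparisons is right. A reader might infer that the secondary endpoint itself is biased. The documents do not support that, because no objective or endpoint concerns the tracer or contrast. The objection does not rescue the procedure-related displays: the SAP chose to report procedure-related events, and its window leaves out acute reactions to the first scan.

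**The events are listed.** All AEs and SAEs go into listings, including those of participants who were not randomized, and with about 12 people a listing is quickly read. So a reader should not conclude that these reactions are lost. A listing still gives no incidence and no denominator.

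**Not every first-scan reaction is left out.** One might infer that all of them are. The table in the working shows otherwise: delayed onset, later worsening and date imputation each bring some of them into the tables.

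**The count is not shown to be half the truth.** That would need equal risk at both scans. Procedure-related AEs also cover other mandated procedures such as venipuncture (Protocol 8.4), and the preferred-term table counts participants rather than scans.

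**Severity.** No procedure-related severity table is planned. The Grade 3 or higher tables with a relatedness condition concern study drug only, so nothing of that kind is understated.

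**The protocol did not promise a procedure-related table.** Protocol 12.6.1 leaves further safety detail to the SAP, and the procedure-related displays are an SAP addition. What was dropped without a declaration is the general all-AE incidence summary.

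**Conclusion.** The point holds as a reporting gap worth correcting. Both procedure-related displays in SAP 5.12.1 exclude reactions to the pre-baseline scan that start before first dose and do not worsen afterwards. The scan concerned is 12 of 24 planned scans (50%), taking 12 participants and two scans each. Separately, the all-AE incidence summary in Protocol 12.6.1 is gone and SAP Section 9 does not say so.

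How many events this will affect cannot be stated, because no reaction rate is given. It could be none. The conclusion rests on the text of SAP 5.12.1. The contents of SAP Section 11 (list of tables) were not in the text available to me, so an additional display there cannot be excluded, but one tabulating pre-dose AEs would contradict 5.12.1. The primary analysis and the study-drug-related AE tables are not affected.

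**What to change.** 1. In SAP 5.12.1, in the overall summary and the system organ class/preferred term table, remove the treatment-emergent restriction from the procedure-related entry and count procedure-related AEs from informed consent.
2. Split that entry into onset before first dose and onset on or after first dose.
3. Show scan-related events over all participants who received at least one tracer administration, including anyone scanned but not dosed. Add that set to SAP 5.1, which has no such population now. Participants with no treatment received can appear in the overall column.
4. Keep the treatment-emergent window for all other AE tables.
5. Either restore the all-AE incidence summary of Protocol 12.6.1 or record its removal in SAP Section 9.

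**Cost.** Two changed displays, one added denominator, and a short rule for identifying which procedure-related events belong to a scan. AEs are already collected from consent, so no new data are needed. The procedure-related count may look slightly less favourable.

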5.12.2 Electrocardiogram-related/Potentially Cardiac-related Treatment-emergent Adverse Events

Participants who have TEAEs with any of the following preferred terms will be identified and reported on a separate summary:

- Electrocardiogram QT prolonged
- Syncope
- Seizure
- Torsade de pointes
- Ventricular tachycardia
- Ventricular fibrillation
- Ventricular flutter
- Ventricular arrhythmia
- Sudden death

QMD Ref: [REDACTED]	Governing QMD: [REDACTED]
Confidentiality Statement	
This document is the property of [REDACTED] without prior approval from [REDACTED]	and may not be duplicated, copied, altered or removed from company or in compliance with [REDACTED]

		Controlled Quality Management Document		
		Sponsor:	Pliant Therapeutics Inc	
		Protocol Number: PLN-74809-IPF-205		
STATISTICAL ANALYSIS PLAN				

5.12.3 Laboratory Data

Descriptive statistics of the observed values and change from baseline (continuous data) will be presented by treatment group and visit for each hematology, coagulation, urinalysis, and serum chemistry parameter. Each measurement (continuous data) will be classed as below, within, or above the normal range, based on normal ranges supplied by the laboratory used. Shift tables in relation to the normal range from baseline to each follow-up visit will be presented. A summary table showing the numbers of participants with at least one abnormal result at any time post-baseline will be presented by laboratory parameter.

Clinical laboratory test parameters will be listed, using the CTCAE grading scale, for individual participants, with values outside the reference ranges flagged. Summary statistics will be calculated for each parameter and summarized by treatment group.

All laboratory data will be listed. Pregnancy test data will be listed only. Abnormal laboratory data will also be listed separately.

5.12.4 Vital Signs

Descriptive statistics for observed values and changes from baseline in the following vital signs will be presented by treatment group and visit:

- Systolic blood pressure (mmHg)
- Diastolic blood pressure (mmHg)
- Heart rate (bpm)
- Temperature (degrees Celsius)
- Body weight (kg)
- Pulse oximetry (%)

5.12.5 Electrocardiogram Data

Descriptive statistics for observed values and changes from baseline in the following ECG variables will be tabulated at each follow-up:

- Heart rate (bpm)
- PR interval (ms)
- RR interval (ms)
- QRS complex (ms)
- QT interval (ms)
- QTc interval (ms) [Fridericia's formula - QTcF]

QMD Ref: [REDACTED]	Governing QMD: [REDACTED]
Confidentiality Statement	
This document is the property of [REDACTED] without prior approval from [REDACTED]	and may not be duplicated, copied, altered or removed from company or in compliance with [REDACTED]

		Controlled Quality Management Document
	Sponsor:	Pitant Therapeutics Inc
	Protocol Number:	PLN-74809-IPF-205
STATISTICAL ANALYSIS PLAN		

Shift tables in relation to the overall interpretation (Normal, Abnormal NCS, and Abnormal CS) from baseline to each follow-up visit will be presented.

A summary table showing the numbers of participants by ECG grades (Section 5.2.15), at any time, will be presented.

All ECG data will be listed.

